### Primary endpoint analysis

Hypothesis: MPO levels after procedure are different between groups.

Hypothesis testing:

- Normality test (Kolmogorov-Smirnov test, Shapiro-Wilk test)

Group comparing:

Continuous variables

- Non-normal distribution: Kruskal-Wallis test with adjustment for multiple comparisons

*Table 6 Myeloperoxidase variables specifications*

Characteristic	Variable name in database	Test
MPO level before procedure	MPOPreOp	Kruskal-Wallis test
MPO level after procedure	MPOPostOp	Kruskal-Wallis test

*Table 7 Myeloperoxidase before and during coronary artery bypass grafting (CABG)*

Variables	off-pump CABG (N=181)	on-pump CABG (N=128)	pump-assisted CABG (N=27)	P Value*
MPO before CABG				0.2904
Nmiss (%)	34 (18.8)	21 (16.4)	9 (33.3)	
Mean±SD	35.8±32.1	39.9±30.6	29.2±14.8	
Min–Max	2.8–237.8	4.0–168.9	5.6–65.4	
Median (IQR)	27.7 (17.0–41.0)	31.0 (19.0–48.7)	29.0 (18.7–34.0)	
MPO after CABG				<.0001
Nmiss (%)	28 (15.5)	26 (20.3)	13 (48.1)	

Date of the document 06 December 2016

Variables	off-pump CABG (N=181)	on-pump CABG (N=128)	pump-assisted CABG (N=27)	P Value*
Mean±SD	96.2±75.3	210.9±138.7	175.0±102.6	
Min–Max	9.1–410.3	16.7–824.6	63.4–374.5	
Median (IQR)	66.5 (41.3–135.8)	184.3 (135.0–250.0)	144.7 (95.0–284.9)	

\* Kruskal-Wallis test, Nmiss – number of missing values, SD – standard deviation, IQR – interquartile range, CABG – coronary artery bypass grafting

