[[contact]](mailto:[contact]) [contact]

Date of the document 06 December 2016

Type of trial	Prospective non-randomised single-centre
Type of research	Exploratory
Timeline	2015-2019
Groups	Off-pump  On – pump  Pump-assisted (on-pump without aortic cross-clamping)
Sample size estimation	> 300 patients
Planned sample size	Average: 300  Off-pump: 100  On-pump: 100  Pump-assisted: 100
Actual sample size	Average: 336  Off-pump: 181 (conversion 6)  On-pump: 128  Pump-assisted: 27
Baseline characteristics comparing	Testing for type of distribution of baseline characteristics:  ANOVA for normal distribution  Kruskal-Wallis test with multiple groups comparison adjustment for non-normal distribution  Chi-squared test or exact Fisher's test for nominal data
Statistics hypothesis testing	ANOVA/ANCOVA for MPO level, troponin I level
Missing Data Handling	Drop observations with missing data
Evaluating of reason of missingness	Hypothesis: Missing data depend on severity of complications  Hypothesis testing with logistic regression model: Missingness = complications

Assessment of Myocardial Ischemic-Reperfusion Injury During Off- and On- Pump CABG  
(ClinicalTrials.gov Identifier: NCT03050489). Corresponding author: [name]  
[[contact]](mailto:[contact]) [contact]

Date of the document 06 December 2016

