## Study Design

Prospective single center non-randomized clinical trial.

**Study Centers:** First Saint Petersburg State Medical University.

**Number of groups:** 3

Intervention:

Group 1: off-pump CABG

Group 2: on-pump CABG

Group 3: pump-assisted CABG (on-pump CABG without aortic cross-clamping)

**Sample size:** >300.

*Table 3 Number of patients*

Intervention	Number of patients	
	Planned	Actual
off-pump CABG	100	181 (175)
on-pump CABG	100	128 (127)
pump-assisted CABG	100	27 (33)
Total	300	336
Conversion	N/A	6

181 patient planned for elective CABG. There were 6 conversions to pump – assisted CABG (on-pump CABG without aortic cross-clamping). 175 received off-pump-CABG. 27 patient planned for elective pump – assisted CABG (on-pump CABG without aortic cross-clamping). 33 pump – assisted CABG were performed.

**Primary Endpoint:** MPO level after operation.

**Secondary Endpoints:** low output syndrome, length of stay in intensive care unit, length of stay in hospital, inotrope and vasopressor agents demand, duration of pulmonary ventilation, end systolic volume, end diastolic volume, ejection fraction, reoperation, renal dysfunction, atrial fibrillation, death during 30 days after CABG, stroke during 30-days after CABG.

Assessment of Myocardial Ischemic-Reperfusion Injury During Off- and On- Pump CABG (ClinicalTrials.gov Identifier: NCT03050489). Corresponding author: [name] [[contact]](mailto:[contact]) [contact]

Date of the document 06 December 2016

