### **Primary objective**

- To compare MPO level before and just after performing coronary anastomosis during off-pump CABG, on-pump CABG and pump-assisted CABG (with cardiopulmonary bypass without aortic cross-clamping)
- To compare TnI level between groups

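### Primary MPO comparison rests on one unadjusted three-group p-value with no pairwise estimates; the ANCOVA does not supply them, and on-pump versus pump-assisted is unresolved

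*Combined protocol and SAP*

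**What the plan says.** The Study Design section names the primary endpoint as "MPO level after operation". The first primary objective is wider: "To compare MPO level before and just after performing coronary anastomosis during off-pump CABG, on-pump CABG and pump-assisted CABG".

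The Primary endpoint analysis section gives the hypothesis, "Hypothesis: MPO levels after procedure are different between groups", and the method, "Non-normal distribution: Kruskal-Wallis test with adjustment for multiple comparisons". No adjustment procedure is named. Table 7 then shows one three-group p for MPO before surgery (0.2904) and one for MPO after (<.0001).

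The synopsis (Table 2) lists "ANOVA/ANCOVA for MPO level, troponin I level". The next section (MPO level, Tables 8–10) fits such a model: log post MPO on log pre MPO, technique, their interaction, number of complications, clamp time, bypass time and operation time. Only F-test rows are reported.

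**The concern.** A three-group p-value says that the techniques are not all alike. It does not say which differ, or by how much. The aim is to compare ischaemic-reperfusion injury across all three techniques, so the pairwise differences are the result that matters. The techniques were also chosen by department and lesion anatomy, so a comparison that ignores pre-operative MPO is weaker than it need be.

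On-pump versus pump-assisted is the contrast nearest to the effect of aortic clamping, since both use bypass. It also has the fewest data. A reader given only the overall p could take it as support for a difference between every pair.

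**Working it through.** **Inputs (Tables 7 and 25).** Patients with post MPO = N minus missing.

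| Technique | Post MPO present | Mean ± SD | Median (IQR) |
|---|---|---|---|
| Off-pump | 181 − 28 = 153 | 96.2 ± 75.3 | 66.5 (41.3–135.8) |
| On-pump | 128 − 26 = 102 | 210.9 ± 138.7 | 184.3 (135.0–250.0) |
| Pump-assisted | 27 − 13 = 14 | 175.0 ± 102.6 | 144.7 (95.0–284.9) |

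The documents give no alpha; two-sided 0.05 is assumed. Everything in steps 1 and 2 is an approximation from summaries of skewed data, on observed cases.

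**1. The plan's overall p.** One-way ANOVA from means and SDs: grand mean 143.8, between-group SS about 819,500 on 2 df, within-group SS about 2,941,700 on 266 df, so F = 409,750 / 11,059 = 37.1, p = 6e-15. On the log scale F is 53 to 59. A Kruskal-Wallis test on data interpolated through each group's minimum, quartiles and maximum gives H = 47.5, p = 5e-11. All agree with <.0001. Off-pump versus on-pump alone gives H = 43.4, p = 4e-11, so that one pair is enough to produce the overall result.

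**2. Pairwise ratios.** Ratio of medians, with SE(log ratio) = 0.69 × √(1/n₁ + 1/n₂). The 0.69 is the square root of the ANCOVA mean square error, 5.77 / 12.13 = 0.476 (Table 9).

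- On/off: 184.3 / 66.5 = 2.77; SE 0.088; 95% CI 2.33–3.29.
- Pump-assisted/off: 144.7 / 66.5 = 2.18; SE 0.193; CI 1.49–3.17.
- On/pump-assisted: 184.3 / 144.7 = 1.27; SE 0.197; CI 0.87–1.87; z = 0.242 / 0.197 = 1.23, p = 0.22.

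Other routes for the last pair:

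- Log SDs from the IQRs, Welch: 1.27 (0.79–2.05), p = 0.29.
- Log moments from mean and SD, Welch: 1.17 (0.84–1.62), p = 0.34.
- Raw means, Welch: difference 35.9, SE √(138.7²/102 + 102.6²/14) = 30.7, CI −28.0 to 99.8, p = 0.26.
- Mann-Whitney on the interpolated data: p = 0.58.

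Power for a true difference of 35.9 with 102 v 14 is about 15% (15 to 23% for SDs from 138.7 to 102.6).

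**3. Whether the ANCOVA supplies the comparison.** Error SS = 51.9 × 0.66 / 0.34 = 100.7; error df = 100.7 / 0.476, about 212; so about 212 + 9 + 1 = 222 patients had both samples. For 2 numerator df, p = (1 + 2F/212)^(−106).

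| Row (Table 10) | Printed F | Printed p | p implied by F |
|---|---|---|---|
| CPBType | 6.6 | 0.0001 | 0.0017 |
| Interaction | 3.6 | 0.0499 | 0.029 |
| LGMPOPreOp | 0.2 | 0.0001 | 0.66 |

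The LGMPOPreOp row also disagrees with itself: mean square 0.9 / 0.476 gives F = 1.9, p = 0.17. Some other rows fail too (clamp time: F 0.05, printed p 0.3, implied 0.82).

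Correct p-values would still leave no usable contrast. Clamp and bypass time largely encode the technique. Complications are counted after the MPO sample is drawn. With the interaction in the model and no centring stated, the Type III technique row refers to log pre MPO = 0, that is 1 ng/ml, below the lowest observed value of 2.8.

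**4. Missing values.** The Missing data analysis section gives the reason for missing post MPO as a result above the upper scale limit. Assume that every missing value exceeds the observed values in its arm.

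- Pump-assisted: the median is the 14th of 27, the highest observed value, 374.5.
- On-pump: the median lies between the 64th and 65th of 128, all within the 102 observed, so between 184.3 and 250.0.
- On/pump-assisted ratio: 184.3 / 374.5 = 0.49 to 250.0 / 374.5 = 0.67.
- Off-pump: the 91st of 181, between 66.5 and 135.8. On/off is then 184.3 / 135.8 = 1.36 to 250.0 / 66.5 = 3.76, still above 1.

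**The case against.** Much can be said for the plan. The study is declared exploratory, the hypothesis matches the named endpoint, and a rank test is reasonable for skewed data. Table 7 prints full summaries by technique, and its overall p is reproducible. These points lower the severity, but exploratory work depends on estimates with intervals, and none is given.

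Several stronger readings are tempting and are not supported:

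- **That pairwise comparison was never planned.** The section promises a multiple-comparison adjustment. What is missing is its name and its results.
- **That baseline MPO is ignored.** The ANCOVA adjusts for it. The fault is in how it is specified and reported.
- **That the before and after tests use different patients.** The sets differ but overlap heavily: about 222 have both samples, against 269 with a post value.
- **That the synopsis contradicts the primary section.** Its ANOVA/ANCOVA entry fits the later models. The gap is that no single analysis is designated primary.
- **That on-pump versus pump-assisted isolates clamping.** On-pump was used for proximal RCA or LCx lesions and pump-assisted for diffuse disease, so clamping is confounded with anatomy.
- **That the documents conceal a null clamping result.** Their stated conclusion concerns bypass, and they make no claim about clamping.

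**Conclusion.** The point holds in this limited form. The primary analysis is an unadjusted overall test, its promised pairwise step is unnamed and unreported, and the ANCOVA does not stand in for it. On observed cases on-pump exceeds off-pump by a ratio of about 2.8 from medians (2.3 from log moments). On-pump versus pump-assisted is unresolved: about 1.2 to 1.3, limits about 0.8 to 2.05, p about 0.2 to 0.6.

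The intervals assume roughly log-normal data and treat missing values as ignorable, which the documents themselves reject. The reversal to 0.49–0.67 is a scenario, not a finding. Pre-operative MPO is also missing in 34, 21 and 9 patients, so some post values may be absent for other reasons. It does show that complete-case ratios alone could mislead on direction. Severity: should-fix.

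**What to change.** 1. Designate one primary model: log post-suture MPO on technique and log pre-operative MPO, without complications, clamp time, bypass time or operation time. Report the baseline-by-technique interaction, with baseline centred, as a secondary check. A log post/pre ratio is not equivalent to this model unless the baseline slope is 1 or log pre MPO stays in as a covariate.
2. Report the three pairwise geometric-mean ratios with 95% confidence intervals and a named adjustment, for example Holm for the p-values, stating whether the intervals are adjusted.
3. Treat over-limit post values as right-censored at the limit for that sample, keep them separate from samples missing for other reasons, and show complete-case results alongside.
4. Keep Kruskal-Wallis as a sensitivity analysis and correct the Table 10 p-values.
5. Word conclusions by contrast, stating that on-pump versus pump-assisted is not resolved and is confounded by anatomy.

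The cost is a revised analysis section, a re-run on existing data and retrieval of the assay limits. The complete-case model has about 222 patients rather than 269. Results are already in the document, so the change should be dated and described as made after the data were seen.

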### Ischemic – reperfusion injury analysis (MPO level)

Hypothesis: MPO level after suture performing depends on length of operation, length of cardiopulmonary bypass, MPO level before procedure and associated with complications

Method of hypothesis testing: ANCOVA

ANCOVA model:  $\text{LGMPOPostOp} = \text{LGMPOPreOp CPBTYPE LGMPOPreOp}^* \text{CPBTYPE}$   
 COMPLICATION AoClamp CPBTime OpTime

Table 8 Variables description

Variable	Description	Note
LGMPOPostOp	Logarithm of MPO level during CABG (after suture performing)	Log – transformation for normal distribution
LGMPOPreOp	Logarithm of MPO level before CABG (after suture performing)	Log – transformation for normal distribution
CPBTYPE	Group of intervention	1 – off-pump CABG 2 – on – pump CABG 3 – pump-assisted CABG
COMPLICATION	Cumulative number of complications	Ordinal variable
AoClamp	Length of aortic cross-clamping, min	Continuous variable
CPBTime	Length of cardiopulmonary bypass, min	Continuous variable
OpTime	Length of procedure, min	Continuous variable
*	Interaction effect	

Table 9 Characteristics of model

Source	Sum of Squares	df	Mean Square	F	p	Eta Square
Model	51.9	9	5.77	12.13	0.0001	0.34

Assessment of Myocardial Ischemic-Reperfusion Injury During Off- and On- Pump CABG (ClinicalTrials.gov Identifier: NCT03050489). Corresponding author: [name] [[contact]](mailto:[contact]) [contact]

Date of the document 06 December 2016

*Table 10 General linear model  $LGMPOPostOp = LGMPOPreOp CPBTYPE LGMPOPreOp*CPBTYPE COMPLICATION AoClamp CPBTime OpTime$*

Source	Sum of Squares (Type III)	df	Mean Square	F	p	Partial Eta Squared
LGMPOPreOp	0.9	1	0.9	0.2	0.0001	0.009
CPBType	6.2	2	3.1	6.6	0.0001	0.06
LGMPOPreOp*CPBTYPE	3.5	2	1.7	3.6	0.0499	0.03
Complication	0.02	1	0.02	0.04	0.6	0.0002
AoClamp	0.03	1	0.03	0.05	0.3	0.0002
CPBTime	0.05	1	0.05	0.1	0.1	0.0004
OpTime	1.3	1	1.3	2.8	0.1	0.01

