#### Ischemic – reperfusion injury analysis (TnI level 1st day after CABG)

Hypothesis: TnI level 1st after CABG depends on length of operation, length of cardiopulmonary bypass, MPO level before procedure and just after suture performing

Method of hypothesis testing: ANCOVA

ANCOVA model:  $LGTnI1 = LGMPOPostOp LGMPOPreOp CPBTYPE LGMPOPreOp*CPBTYPE AoClamp CPBTime AoClamp*CPBTime OpTime CPBTime* OpTime AoClamp*OpTime$

*Table 11 Variables descriptions*

Variable	Description	Note
TnI1	Troponin I level 1 st day after procedure	Continuous variable
LGMPOPostOp	Logarithm of MPO level during CABG (after suture performing)	Log – transformation for normal distribution
LGMPOPreOp	Logarithm of MPO level before CABG (after suture performing)	Log – transformation for normal distribution
CPBTYPE	Group of intervention	1 – off-pump CABG 2 – on – pump CABG 3 – pump-assisted CABG
AoClamp	Length of aortic cross-clamping, min	Continuous variable
CPBTime	Length of cardiopulmonary bypass, min	Continuous variable
OpTime	Length of procedure, min	Continuous variable
*	Interaction effect	

*Table 12 Characteristics of model*

Source	Sum of Squares	df	Mean Square	F	p	Eta Square

Assessment of Myocardial Ischemic-Reperfusion Injury During Off- and On- Pump CABG (ClinicalTrials.gov Identifier: NCT03050489). Corresponding author: [name] [[contact]](mailto:[contact]) [contact]

Date of the document 06 December 2016

Model	249.3	14	17.8	10.4	0.0001	0.44
-------	-------	----	------	------	--------	------

*Table 13 General linear model characteristics*  $LGTnI1 = LGMPOPostOp LGMPOPreOp CPBTYPE$   
 $LGMPOPreOp*CPBTYPE AoClamp CPBTime AoClamp*CPBTime OpTime CPBTime* OpTime$   
 $AoClamp*OpTime$

Source	Sum of Squares (Type III)	df	Mean Square	F	p	Partial Eta Squared
LGMPOPostOp	2.0	1	2.6	1.2	0.3	0.006
LGMPOPreOp	0.8	1	0.8	0.5	0.5	0.002
AoClamp	2.3	1	2.3	1.4	0.2	0.007
CPBTime	2.2	1	2.2	1.3	0.3	0.007
OpTime	23.3	1	23.3	13.6	0.0003	0.07
CPBType	3.9	2	1.9	1.1	0.3	0.01
CPBTime*OpTime	0.7	1	0.7	0.4	0.5	0.002
AoClamp*CPBTime	0.4	1	0.4	0.22	0.6	0.001
AoClamp*OpTime	3.5	1	3.5	2.1	0.2	0.01
LGMPOPostOp*CPBTYPE	4.1	2	2.1	1.2	0.3	0.01
LGMPOPreOp*CPBTYPE	0.4	2	0.2	0.1	0.9	0.001

**Summary:** troponin I level 1st day postoperatively depends on length of operation

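### The adjusted technique rows of Tables 10 and 13 compare the CABG techniques at an MPO of 1 ng/ml, below every measured value, because log-MPO interacts with technique and no centring is stated

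*Combined protocol and SAP*

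**What the plan says.** The primary endpoint section sets out "Hypothesis: MPO levels after procedure are different between groups" and assigns it to the Kruskal-Wallis test (Table 6). The primary objective also includes "To compare TnI level between groups". The synopsis (Table 2) gives the hypothesis-testing method as "ANOVA/ANCOVA for MPO level, troponin I level".

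Two pooled ANCOVAs contain technique (CPBTYPE):

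- **MPO model:** "LGMPOPostOp} = \text{LGMPOPreOp CPBTYPE LGMPOPreOp}^* \text{CPBTYPE}$ COMPLICATION AoClamp CPBTime OpTime".
- **Day-1 TnI model:** its formula begins "LGTnI1 = LGMPOPostOp LGMPOPreOp CPBTYPE LGMPOPreOp*CPBTYPE AoClamp CPBTime" and continues with the times and their products. The written formula has only the pre-operative MPO interaction. Table 13 also prints a post-suture MPO by technique row.

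Table 8 describes the baseline covariate as "Logarithm of MPO level before CABG (after suture performing". That label places one sample both before surgery and after suturing and needs tidying. What matters here is that it is a plain logarithm. No centring, no reference MPO value and no adjusted means appear anywhere. Tables 10 and 13 head their tests "Sum of Squares (Type III".

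**The concern.** Once a model has a separate MPO slope for each technique, the gap between techniques depends on the MPO level at which it is read. A Type III technique row reads it where the covariate is zero. If that point lies far outside the data, the row no longer asks whether techniques differ for patients like those treated.

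Two errors follow. If slopes differ, the row can be significant although techniques agree at ordinary MPO values. If slopes are equal, the row must estimate a difference at a remote point and becomes very imprecise. These rows are the only covariate-adjusted technique tests for MPO and TnI in the document, so a reader is likely to consult them.

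**Working it through.** **1. Printed technique rows.** The MPO model line in Table 9 reads "Model 51.9 9 5.77 12.13 0.0001 0.34".
- Residual mean square = 5.77/12.13 = 0.476. Residual sum of squares = 51.9 × 0.66/0.34 = 100.7. Residual df ≈ 212, so about 222 patients.
- Table 10, CPBType: F = 3.1/0.476 = 6.5 (printed 6.6). On 2 and 212 df, F = 6.6 gives p = 0.0017; the table prints 0.0001.
- Table 10, interaction: F = 3.6 gives p = 0.029; the table prints 0.0499.
- Tables 12–13: residual mean square = 17.8/10.4 = 1.71, about 200 patients. CPBType F = (3.9/2)/1.71 = 1.14, p = 0.32 (printed 1.1 and 0.3).
- The Table 13 rows sum to 14 df, matching Table 12. Both MPO interactions were therefore fitted.

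**2. Where the row compares techniques.** For technique g the model is a_g + b_g × log(MPO) plus common terms. The Type III CPBTYPE hypothesis is a_1 = a_2 = a_3, that is, equality at log(MPO) = 0. MPO is expressed in ng/ml, so this is 1 ng/ml in any log base. In Table 13, pre-operative and post-suture MPO are both set to 1 ng/ml.

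**3. Distance from the data.** From Table 7, log mean ≈ ln(median) and log SD ≈ ln(Q3/Q1)/1.349:

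| | Off-pump | On-pump | Pump-assisted |
|---|---|---|---|
| Pre-operative minimum, ng/ml | 2.8 | 4.0 | 5.6 |
| Log mean / SD | 3.32 / 0.65 | 3.43 / 0.70 | 3.37 / 0.44 |
| SDs from mean to 1 ng/ml | 5.1 | 4.9 | 7.6 |
| Post-suture minimum, ng/ml | 9.1 | 16.7 | 63.4 |
| SDs from mean to 1 ng/ml | 4.8 | 11.4 | 6.1 |

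**4. Cost in precision (times omitted).** A group's standard error at 1 ng/ml is √(1 + mean²/SD²) times that at its own mean: 5.2, 5.0 and 7.7 for pre-operative MPO. With an assumed 125 off-pump and 85 on-pump complete cases, the standard error of the on/off difference is √0.476 × √(5.19²/125 + 5.02²/85) = 0.49. At the group means it is √0.476 × √(1/125 + 1/85) = 0.10. The crude on/off contrast, ln(184.3/66.5) = 1.02, is only about 2 standard errors at 1 ng/ml.

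**5. Effect of unequal slopes.** With 125/85/12 patients, n × SD² of log-MPO is 53.2, 41.4 and 2.4. If only the on-pump slope differs, by d, the interaction sum of squares gains d² × 41.4 × 55.6/97.0 = 23.7 d². The excess implied by the printed F is (3.6 − 1) × 2 × 0.476 = 2.48, so d ≈ 0.32. Lines equal at the overall log mean of 3.37 are then 0.32 × 3.37 = 1.08 apart at 1 ng/ml, about 2.2 standard errors.

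**6. Simulation.** MPO model, alpha 0.05 assumed, about 222 patients; share of runs with CPBTYPE p < 0.05. Ranges cover repeat runs, splits of 124/86/12 or 125/85/12, and the assumed times.

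| Scenario | Uncentred | Centred |
|---|---|---|
| *Times omitted* | | |
| No effect, equal slopes | about 5% | about 5% |
| No difference at mean MPO, slope difference 0.20 | 21–22% | about 5% |
| Same, 0.32 | 46–49% | 5–6% |
| Same, 0.40 | 67–68% | 5–6% |
| Shift of 0.5 residual SD, equal slopes | 9–10% | 91% |
| Shift equal to Table 7 median ratios, equal slopes | 43–44% | 100% |
| *Times kept, distributions assumed* | | |
| No difference at mean MPO, slope difference 0.32 | 39% | 4% |
| Shift of 0.5 residual SD, equal slopes | 7–8% | 11–26% |
| Shift equal to Table 7 median ratios, equal slopes | 29–38% | 65–99% |

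The document gives no distribution of the times. The power ranges with times kept assume bypass of 80–100 min (SD 20–30) and clamp time of about 0.6 of bypass time (residual SD 8). Dropping the interaction instead of centring gives 11–27% for the 0.5 SD shift.

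For TnI, with both interactions, times omitted and a true difference equal to the ratios of the day-1 medians (0.4, 3.1, 1.4), power is 14–17% uncentred and 100% centred.

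**The case against.** **The row is not the plan's technique test.** This stands. Kruskal-Wallis is the stated primary test for MPO (p < .0001), and day-1 TnI by technique is reported at p < .0001 in the secondary endpoint section. Neither depends on the ANCOVAs. The hypotheses written above the two models name durations and MPO (plus complications in the MPO model), not technique.

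**No stated conclusion rests on it.** This also stands. The TnI summary names length of operation and does not claim that technique is irrelevant. In Table 10 the technique row is significant, in agreement with Kruskal-Wallis.

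**Centring would not give a usable technique effect.** This largely stands. By definition off-pump patients have no bypass or clamp time and pump-assisted patients have no clamp time, so a model holding those times constant still extrapolates. With the times kept, most of the apparent power gain for a moderate shift disappears. The false-positive contrast remains (39% against 4%).

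**The slope evidence is weak.** Partly right. Table 10's F and p values disagree, so 0.32 is an assumption. In Table 13 the interactions have p = 0.9 and 0.3, so for TnI the argument is about power, not false rejection.

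**Uncentred coding is inferred.** True, but the variables are defined as plain logarithms and nothing else is stated. Likewise, values below every patient means below every measured value. For missing post-suture results the document suspects readings above the assay's upper limit, the opposite end.

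The exploratory label does not answer the point, because the rows are printed with p values.

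**Conclusion.** The concern holds for the CPBTYPE rows of Tables 10 and 13 and goes no further. As specified, they test technique at 1 ng/ml, about 5 to 8 SD below the pre-operative log means. That conclusion is algebraic, given plain-log coding. The size of the harm rests on assumptions: complete-case splits, log-normal MPO, alpha 0.05, and a slope difference near 0.32 for the 40–50% false-rejection figure. With equal slopes type I error is kept and only power is lost.

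Three stronger readings are tempting and not supported:
- That the primary comparison is invalid: the Kruskal-Wallis results are untouched.
- That Table 13 has been shown to hide a real adjusted technique effect: its p = 0.3 is uninformative either way, and post-suture MPO and the times are also tied to technique.
- That centring restores 91–100% power: this holds only with clamp and bypass times omitted.

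The single-technique TnI models are not affected. The on-pump formula prints CPBTYPE but Table 16 has no such row, and the other two have no interaction.

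**What to change.** - **MPO model:** enter LGMPOPreOp minus its overall mean (about ln 29), or take the technique test from the model without the interaction and report the interaction separately as a check on slopes.
- **TnI model:** do the same for LGMPOPreOp, and for LGMPOPostOp if its interaction stays. Make the written formula agree with the fitted one.
- **Reporting:** state the MPO value used, and give pairwise adjusted ratios with 95% CIs at that value in place of the present technique rows. Add that Table 13's CPBType p = 0.3 is not evidence of no technique effect.
- **Checking:** re-derive Table 10's F and p values in the same run.

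The cost is one line of code per model, a re-run on existing data and revised SAP wording. Centring leaves the fit, residuals and interaction rows unchanged. An interpretable adjusted technique effect also needs a separate decision on the clamp and bypass time covariates.
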